9.2. Sample Size Determination

The primary efficacy parameter is the absence of a headache of moderate/severe intensity within 24 hours after taking double-blind study intervention during the prodrome. Based on the assumption of a response rate of 64% for the placebo group and 80% for the ubrogepant 100 mg group, 240 participants in each study intervention will provide at least 95% power to detect the

above intervention difference at the 2-sided 5% significance level. The nQuery Advisor 7.0 was used for the power calculation.

A blinded sample size re-estimation has been performed as planned. Given that 7% of participants had no determinable primary endpoint as observed based on the data cut of July 5, 2021, approximately 516 participants will be randomized to maintain the effect sample size of 480 participants.

The actual power will be higher with the crossover design as some participants will contribute 2 qualifying prodrome events during the double-blind treatment period.

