**Table 3. Missing data handling at prodrome level and within prodrome level**

Analyses	Missing prodrome event	Indeterminable endpoints within prodrome event level
Primary analysis	Ignore and no imputation	Set as missing and no imputation
Sensitivity analysis 1: NRI for indeterminable endpoints	Ignore and no imputation	Set as non-responder
Sensitivity analysis 2: imputation under MAR for indeterminable endpoints	Ignore and no imputation	Sequential multiple imputation
Sensitivity analysis 3: imputation under MNAR for missing prodrome events and under MAR for indeterminable endpoints	MNAR	Sequential multiple imputation
Sensitivity analysis 4: Period 1 only	Ignore and no imputation	Set as missing and no imputation

For sensitivity analysis 2, indeterminable endpoints will be imputed using multiple imputation under MAR. The determinations of the efficacy endpoints are described in the corresponding endpoints sections. Specifically for the primary endpoint, for a participant who has not experienced headache of moderate/severe intensity by time  $t_j$  after study intervention and has missing headache severity assessment at the next timepoint  $t_{j+1}$ , whether the participant will experience headache of moderate/severe intensity at  $t_{j+1}$  will be imputed based on other participants on the same treatment who have not experienced headache of moderate/severe intensity by time  $t_j$  but have observed headache severity assessment at  $t_{j+1}$ . Base will be used in the imputation logistic model. Base is a continuous variable denoting the percentage of absence of moderate/severe headache within time  $t_{j+1}$  during the screening period. So firstly, the missing headache severity assessment by time  $t_1$  will be imputed. The missing headache by the following timepoints (2, 3, 4, 6, 8, 24, and 48 hours) will be imputed step by step similarly. One hundred datasets will be imputed.

For sensitivity analysis 3, indeterminable endpoints will be imputed using multiple imputation under MAR, and endpoints in missing prodrome events will be imputed under MNAR. One hundred datasets will be imputed.

- For participants who go through the 60-day double-blind treatment period with only one qualifying prodrome event due to lack of qualifying event or having an event but with no headache assessment, the missing data for the missing qualifying prodrome event will be considered as missing at random using multiple imputation.

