**Figure 2. Determination of absence of moderate/severe headache within 24 hours (responder)**

The primary comparison between study intervention groups will be analyzed using a GLMM model with repeated measurements based on determinable data on the primary efficacy endpoint data. The GLMM model assumes a binary distribution for the response and uses a logit link. The analysis model will include study intervention period, and treatment as categorical fixed effects. An unstructured covariance matrix will be selected for the covariance matrix of the residual effect for the repeated measurements (corresponding to the two qualifying prodrome events) within a participant. The treatment difference in terms of odds ratio between ubrogapant 100 mg and placebo will be estimated from the GLMM model.

The carryover effect will be tested although no or very minimum carryover effect is expected as the minimum 7-day washout period is much longer than the 5 times of half-life. A similar GLMM model will be fitted to examine the carryover effect. The model includes period and treatment as categorical fixed effects, and period by treatment as interaction effect. The carryover effect will be tested using the confounded period by treatment interaction at 0.05 significance level. If the carryover effect is significant, the analysis will use the first period only data for the primary efficacy analysis. For sensitivity analysis purpose, first period only data analysis will be performed regardless of the significance level of the carryover effect using logistic regression model with treatment effect.

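### The Period-1-only analysis of the primary endpoint is planned with treatment alone and leaves out the screening headache rate (Base) that the SAP already derives; adding it is a cheap precision gain of uncertain size

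*SAP*

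**What the plan says.** The main analysis of the primary endpoint is a two-period GLMM (SAP 8.3.3): "The analysis model will include study intervention period, and treatment as categorical fixed effects". The same section adds that "first period only data analysis will be performed regardless of the significance level of the carryover effect using logistic regression model with treatment effect". This is sensitivity analysis 4 in SAP Table 3.

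If the carryover test is significant at 0.05, SAP 8.3.3 makes the Period-1 data the primary analysis. That sentence names no model. SAP 8.4.1 plans a Period-1 logistic regression for the first and third secondary endpoints and lists no terms.

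SAP 8.2 defines a screening covariate for the imputation model: "Base is a continuous variable denoting the percentage of absence of moderate/severe headache within time" of the timepoint being imputed. Neither the GLMM nor the stated Period-1 model uses it.

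**The concern.** In the two-period analysis each participant with two events serves as their own control, so a participant-level covariate has little to add. Period 1 alone is different. It is a 1:1 parallel-group comparison, and differences between participants in their tendency to develop moderate/severe headache go straight into the error.

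Base summarises that tendency on the same outcome, before randomisation, from the 3 to 16 screening events required for entry (Protocol 4.1, inclusion criterion 2.06). It should therefore be available for nearly everyone. By placing it in the imputation model, the SAP already treats it as a predictor. Leaving it out of the Period-1 model costs precision in the one planned analysis without within-participant control, and that analysis would carry the primary claim if the carryover test were significant.

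**Working it through.** **Inputs from the documents** (Protocol 9.2, unless noted)
- Rates: "Based on the assumption of a response rate of 64% for the placebo group and 80% for the ubrogepant 100 mg group".
- Size: "240 participants in each study intervention will provide at least 95% power to detect the" difference, at the two-sided 5% level.
- Inflation: "Given that 7% of participants had no determinable primary endpoint as observed based on the data cut of July 5, 2021", so "approximately 516 participants will be randomized to maintain the effect sample size of 480 participants".
- Screening events per participant: m = 3 to 16; the distribution is not given.

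**Assumed, because neither document gives it**
- Within-participant correlation of the response: ρ = 0.1 to 0.4.
- Correlation between screening and double-blind propensity: 1, then 0.7.
- 240 determinable Period-1 results per arm.

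**1. The plan's own figures.** The stated calculation is a two-group one, so it describes the Period-1 comparison directly. Power = Φ{[0.16 − 1.96·√(2·0.72·0.28/240)] / √[(0.64·0.36 + 0.80·0.20)/240]} = Φ{(0.16 − 0.0803)/0.0403} = Φ(1.975) = 97.6%. It is 96.9% with a continuity correction and 97.0% by Fisher's exact test. All agree with at least 95%. The inflation also reproduces: 480/0.93 = 516.1.

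**2. Precision given up, by formula.** The squared correlation between a mean of m screening events and one new event is R² = ρ²m / [1 + (m − 1)ρ]. The share of effective sample size given up is R², and the adjusted effective size is n/(1 − R²).

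| ρ | m = 3 | m = 16 |
|---|---|---|
| 0.1 | 0.03/1.2 = 2.5% | 0.16/2.5 = 6.4% |
| 0.2 | 0.12/1.4 = 8.6% | 0.64/4.0 = 16.0% |
| 0.3 | 0.27/1.6 = 16.9% | 1.44/5.5 = 26.2% |
| 0.4 | 0.48/1.8 = 26.7% | 2.56/7.0 = 36.6% |

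**3. Check by simulation** (3,000 trials per scenario, 240 per arm, 64% vs 80%, logit-normal participant effect, logistic model with and without Base). The share given up was taken both from the z ratio and from the variance of the standardised difference. Across the two measures it was 2%-4% at ρ = 0.1, 8%-11% at 0.2, 15%-22% at 0.3 and 23%-31% at 0.4. This is the same order as the formula and somewhat lower at the top.

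**4. A smaller effect** (600 trials per scenario, 480 participants, about 6 screening events, odds ratio 1.5).
- Logit SD between participants 1.0: mean z goes from 2.014 to 2.102. (2.102/2.014)² − 1 = 9% more participants, so 1 − (2.014/2.102)² = 8% given up. Power goes from 53% to 56%.
- Logit SD 1.6: mean z goes from 2.009 to 2.241, which is 24% more participants or 20% given up. Power goes from 54% to 62%.

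At a 64% rate these SDs correspond to ρ of about 0.17 to 0.31.

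**5. If screening predicts less well.** With a propensity correlation of 0.7 and m = 3 to 8, the share given up falls to about 4% (ρ = 0.2), 8% (ρ = 0.3) and 9%-11% (ρ = 0.4).

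**6. What this means for power** (240 per arm before adjustment; 76% is an assumed smaller effect)

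| R² | Effective n per arm | 64% vs 80% | 64% vs 76% |
|---|---|---|---|
| 0 | 240 | 97.6% | 82.0% |
| 0.05 | 253 | 98.1% | 83.9% |
| 0.09 | 264 | 98.5% | 85.5% |
| 0.24 | 316 | 99.5% | 91.0% |

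**7. Two-period model.** In the step 4 simulation, using an exchangeable GEE for the two periods, adding Base left mean z at 3.19. With 20% of participants contributing a single event it went from 3.15 to 3.18. There is essentially nothing to gain there.

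**The case against.** The strongest reply is that nothing is broken. The treatment-only model is valid and is easy to compare with the main analysis. SAP 8.3.4 keeps the population-level summary the same across the sensitivity estimands, and Table 4 states that summary as an odds ratio. A logistic model with Base returns a conditional odds ratio, so a difference from the main result could mix carryover with non-collapsibility. Avoiding this needs standardisation, a matching variance and a rule for missing Base. This stands as a cost. It does not defeat the proposal, because standardising restores the marginal odds ratio.

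Predictive value is also open to doubt. Protocol 6.5.3 allows rescue for headache of any intensity in screening, but in the double-blind period bars it for mild headache within 24 hours of dosing. SAP Table 4 counts rescue within 24 hours as non-response, and SAP 10.2 derives absence of moderate/severe headache differently in screening. This stands too. Base can be expected to be prognostic, but the documents do not show that it is strongly so.

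The practical weight is limited as well. Power at the design rates is already 97.6%, sensitivity analyses lie outside the testing sequence in SAP 12.0, and SAP 8.3.3 expects little or no carryover.

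A reader might infer that every Period-1 model is treatment-only. The SAP says so only for the primary endpoint's sensitivity analysis; the fallback and the secondary models are unspecified. A reader might also want Base in all of them. As defined, it is a moderate/severe rate and does not match the third secondary endpoint. A matching any-intensity headache-free rate would be confined to at most 25%, because entry requires headache after at least 75% of screening events (all of them if only three are recorded).

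**Conclusion.** The point holds as a cheap improvement, not as an error. The stated Period-1 analysis of the primary endpoint omits a pre-randomisation covariate that the SAP already derives. The models for the carryover fallback and the secondary Period-1 analyses still have to be specified.

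The size rests on assumptions. The share of effective sample size given up is 2.5% to 37% by formula for ρ = 0.1 to 0.4 and 3 to 16 events. It is about 8% to 20% for logit SD 1.0 to 1.6 with about 6 events, and about 4% to 11% if screening and double-blind propensities correlate only 0.7. A reader might take 9% to 24% as the established loss. That range is the equivalent increase in participants under one set of assumed SDs, and the documents supply no correlation that would fix it. At 64% vs 80% the gain in power is about one to two percentage points; it is larger for smaller effects.

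**What to change.** In SAP 8.3.3, add Base within 24 hours as a covariate in the Period-1-only logistic model for the primary endpoint, and state that the same model applies if Period 1 becomes the primary analysis after the carryover test. In SAP 8.4.1, write out the Period-1 model terms and add Base within 48 hours for the first secondary endpoint. In both, average the fitted probabilities over the observed distribution of Base under each treatment. Report the resulting marginal odds ratio with a variance method that matches the standardisation, so that it agrees with Table 4. State a rule for participants whose Base cannot be determined.

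Leave the two-period GLMM unchanged, and do not use this Base for the third secondary endpoint. No new data are needed. The cost is one covariate plus the standardisation step and its variance. It should be settled before unblinding, since a covariate added afterwards would look selective.

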#### **8.3.4 Sensitivity Analyses**

As alternative estimands for the primary study objective, the treatment condition, population, variable, and population-level summary will be the same as those in the primary estimand. However, the way to handle the discontinued participants with only one qualifying prodrome event and the approach to handle missing data within a prodrome event will be different. For participants who discontinued the double-blind treatment period with only one qualifying prodrome event, the missing data for the second qualifying prodrome event will be handled same as the primary analysis or imputed under MNAR. For indeterminable primary endpoint due to missing data within a prodrome

event, the primary endpoint will be set as missing, non-responder, or imputed using sequential multiple imputation. Missing data handling is described in Section 8.2.

A sensitivity analysis will impute participants with indeterminable status or missing headache occurrence within 24-hours recall as non-responders for the qualifying prodrome event. Data will be analyzed using the same primary GLMM model.

An additional sensitivity analysis will use multiple imputation approaches to impute the missing headache occurrence status within 24 hours under MAR for each qualifying prodrome event with indeterminable endpoints. Another sensitivity analysis will assume missing prodrome events as missing MNAR. The treatment difference between ubrogepant 100 mg and placebo will be estimated from the GLMM model for each imputed data set and combined across imputations to obtain the multiple imputation estimate using standard multiple imputation techniques applied to log odds ratio.

Analyses using only first period data will also be performed as a sensitivity analysis as mentioned in the previous section.

## **8.4 Secondary Efficacy Analyses**

### **8.4.1 Secondary Efficacy Analyses**

The secondary hypotheses are stated as follows:

Secondary null hypothesis 1: Ubrogepant 100 mg is the same as placebo in the acute treatment of migraine when administered during the prodrome, as measured by the proportion of participants who do not develop headache of moderate/severe intensity within 48 hours after taking the double-blind study intervention during the prodrome.

Secondary alternative hypothesis 1: Ubrogepant 100 mg is different from placebo in the acute treatment of migraine when administered during the prodrome, as measured by the proportion of participants who do not develop headache of moderate/severe intensity within 48 hours after taking the double-blind study intervention during the prodrome.

Secondary null hypothesis 2: Ubrogepant 100 mg is the same as placebo in the acute treatment of migraine when administered during the prodrome, as measured by the proportion of participants who are able to function normally over 24 hours after taking the double-blind study intervention during the prodrome.

[figure not shown]
Secondary alternative hypothesis 2: Ubrogepant 100 mg is different from placebo in the acute treatment of migraine when administered during the prodrome, as measured by the proportion of participants who are able to function normally over 24 hours after taking the double-blind study intervention during the prodrome.

Secondary null hypothesis 3: Ubrogepant 100 mg is the same as placebo in the acute treatment of migraine when administered during the prodrome, as measured by the proportion of participants who do not develop headache of any intensity within 24 hours after taking the double-blind study intervention during the prodrome.

[figure not shown]
Secondary alternative hypothesis 3: Ubrogepant 100 mg is different from placebo in the acute treatment of migraine when administered during the prodrome, as measured by the proportion of participants who do not develop headache of any intensity within 24 hours after taking the double-blind study intervention during the prodrome.

Estimands for the secondary objective will be assessed using three secondary endpoints. The population and population-level summary, as well as the approach to handle intercurrent events will be the same as those for the primary endpoint except that rescue medication is part of the treatment condition such that it is not an intercurrent event for FDS. The determination of the first and third secondary endpoints are shown in [Figure 3](#) and [Figure 4](#).

**Figure 3. Determination of absence of moderate/severe headache within 48 hours (responder)**

**Figure 4. Determination of absence of any intensity headache within 24 hours (responder)**

The first and third secondary endpoints (i.e., the absence of a headache of moderate/severe intensity within 48 hours and absence of a headache of any intensity within 24 hours after taking double-blind study intervention during the prodrome) will be analyzed using a GLMM model based on observed data similar to the one used for the analysis of the primary endpoint.

A sensitivity analysis will impute participants with indeterminable status as non-responders. An additional sensitivity analysis will use the multiple imputation approach described for the primary endpoint to impute the missing headache occurrence status within 24 hours/48 hours for the participant for each qualifying prodrome event with an unknown status of headache occurrence within 24 hours/48 hours after taking double-blind study intervention.

Another sensitivity analysis will assume missing prodrome events as MNAR. Analyses using only first period data will also be performed as a sensitivity analysis using logistic regression model.

The second secondary endpoint, i.e., ability to function normally over 24 hours after taking double-blind study intervention during the prodrome, includes the repeated measures of dichotomized FDS response at each postdose timepoint over 24 hours. The dichotomized response takes value 1 if the participant records no disability, able to function normally on the FDS, and takes value 0 otherwise. The repeated binary responses will be analyzed using a GEE model with a logit link. The GEE model will include period, treatment, time, treatment-by-time interaction as categorical fixed effects, predose baseline FDS score for the period, and predose baseline-by-time interaction as covariates. An unstructured working correlation matrix will be used for the repeated measures within each participant. If the unstructured correlation matrix does not converge, an unstructured correlation matrix or a working m-dependent ( $m=6$ ) correlation matrix (if unstructured correlation matrix failed) will be used within each prodrome event and the two prodrome events will be assumed to be independent. The treatment effect will be expressed in terms of the geometric mean of the odds ratios of ubrogapant 100 mg

[figure not shown]
relative to placebo estimated at the scheduled timepoints within 24 hours after taking double-blind study intervention.

As described in Section 12.0, a serial gatekeeping procedure will be used to control the overall type I error rate at the 0.05 level for multiple comparisons across the primary and three secondary efficacy endpoints.

## **8.5 Additional Efficacy Analyses**

[figure not shown]
The determination of absence of a headache of any intensity, moderate/severe and severe headache by each timepoint are shown in [Figure 5](#), [Figure 6](#), and [Figure 7](#). When a headache is collected in a 24-hour recall, the missing headache intensity at prespecified hours before the recalled headache time is assumed to be less severe than the recalled headache intensity.

**Figure 5. Determination of absence of any intensity headache by T hours (1, 2, 3, 4, 6, 8, 48 hours) (responder)**

[figure not shown]

**Figure 6. Determination of absence of moderate/severe headache by T hours (1, 2, 3, 4, 6, 8 hours) (responder)**

**Figure 7. Determination of absence of severe headache by T hours (1, 2, 3, 4, 6, 8, 24, 48 hrs) (responder)**

The absence of a headache of any intensity by each timepoint after taking double-blind study intervention will be analyzed using the same GLMM model as primary endpoint.

Similar analyses will be performed for the absence of a headache of moderate/severe intensity and absence of severe headache by timepoint. Kaplan-Meier curves for time to development of any intensity headache (or rescue medication taken), time to development of moderate/severe headache, time to development of severe headache within 48 hours will be produced by treatment and compared between treatment using the log-rank test. In addition, Kaplan-Meier curves for time to development of moderate/severe headache (or rescue medication taken) and time to development of severe headache within 48 hours (or rescue medication taken) will be produced. Hazard ratio will be estimated from cox proportional hazard model with treatment and period factors.

For each of the 5 most common individual prodrome symptoms, the absence of any intensity, absence of moderate/severe intensity, absence of severe intensity at each timepoint will be analyzed using GLMM with additional predose baseline prodrome symptom intensity category. In addition, prodrome symptoms will be summarized by descending frequency in ubrogепant group and by intensity at predose. Same GLMM model as the primary endpoint will be performed for the absence of any intensity, absence of moderate/severe intensity, absence of severe intensity nonheadache migraine symptom at each timepoint after a headache of any intensity is reported. The absence of aura at timepoint will be analyzed using GLMM model with additional predose baseline aura status. Kaplan-Meier curves for time to absence of each of the 5 most common individual prodrome symptoms will be produced by treatment and compared between treatment using the log-rank test. Kaplan-Meier curves will also be generated censoring data collected after rescue medication for migraine associated symptoms. Hazard ratio will be estimated from cox proportional hazard model with treatment and period factors.

The observed proportions of participants who used rescue medication within 24 and 48 hours after taking double-blind study intervention will be summarized and analyzed using the same GLMM model as primary endpoint. The treatment comparisons will be conducted using the primary model. Kaplan-Meier curves for time to rescue medication use within 48 hours after taking double-blind study intervention will also be produced by

treatment and compared by log rank test. Hazard ratio will be estimated from cox proportional hazard model with treatment and period factor.

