## 2.4 Sample Size Determination

The primary efficacy parameter is the absence of a headache of moderate/severe intensity within 24 hours after taking double-blind study intervention during the prodrome. The original sample size of 600 participants randomized is based on the assumption of a response rate of 64% for the placebo group and 80% for the ubrogепant 100 mg group, 240 participants in each study intervention will provide at least 95% power to detect the above intervention difference at the two-sided 5% significance level. The nQuery

Advisor 7.0 was used for the power calculation. Assuming 20% of randomized participants will not experience a qualified prodrome event during the double-blind treatment period, 300 participants will be randomized to each treatment sequence.

A blinded sample size re-estimation has been performed as planned. Given that only 7% of participants, rather than the 20% originally assumed, had no determinable primary endpoint as observed based on the data cut of July 05, 2021, it was re-estimated that approximately 516 participants will need to be randomized to maintain the effective sample size of 480 participants.

The actual power will be higher with the crossover design as some participants will contribute 2 qualifying prodrome events during the double-blind treatment period.

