A single-item measure assessing activity limitation based on a 24-hour recall will be administered as an additional health outcome measure. The measure will be used to evaluate activity limitation with a 5-level response ranging from "Not at all limited – I could do everything" to "Extremely limited." The measure will be administered at 24 hours after taking double-blind study intervention.

The following are general considerations for efficacy analyses:

- Efficacy analyses will be performed based on mITT population.
- Continuous variables will be summarized by number of participants with observed values (n), mean, standard deviation (SD), median, 1st and 3rd quartiles (Q1, Q3), minimum (min), and maximum (max).
- Categorical variables will be summarized by number of participants with observed values or events and percentages based on the specified population.
- The efficacy analyses will be performed using a GLMM in the observed binary response variable unless an imputation method is specified.
- The least squares mean (LSMEAN) estimates of the treatment effects for the primary and secondary endpoints alongside its 95% CI will be presented.

- All statistical hypothesis tests will be performed at the 2-sided 5% significance level.
- Efficacy analyses will be presented by treatment or study intervention randomized (placebo or ubrogepant 100 mg).

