## **10.0 Other Analyses**

### **10.1 Additional Health Economics Outcomes Research (HEOR) Analyses**

Satisfaction with study medication responder is defined as response to the Satisfaction with Study Medication question of 'Satisfied' or 'Extremely Satisfied.' The same GLMM model for the primary endpoint will be performed at 8 hours and 24 hours, separately. Descriptive statistics at 8 hours and 24 hours after taking double-blind study intervention will be presented by study intervention.

The ordinal activity limitation will be analyzed using Cochran-Armitage trend test. In addition, responder analyses will be performed using the same GLMM model. A participant will be defined as a responder if the participant records not at all limited - I could do everything or a little limited, and a non-responder otherwise. Descriptive statistics at 24 hours taking double-blind study intervention will be presented by study intervention.

For FDS, by timepoint analysis will be performed using the same primary GLMM model with an additional covariate of predose baseline FDS score at 1, 2, 3, 4, 6, 8, and 24 hours. Additional endpoint will be defined as a responder if a participant records no disability, able to function normally at all the observed timepoints FDS (1, 2, 3, 4, 6, 8, and 24 hours postdose), and a non-responder otherwise. The data will be analyzed using the same primary GLMM model with an additional covariate of predose baseline FDS score.

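### The log-rank, Cox and Cochran-Armitage analyses ignore that both treatments are given to the same participants, so their p-values and intervals are miscalibrated

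*SAP*

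**What the plan says.** SAP 8.5 plans Kaplan-Meier curves for time to headache of any, moderate/severe and severe intensity. These "will be produced by treatment and compared between treatment using the log-rank test". The same comparison is planned for time to absence of each of the five most common prodrome symptoms. For time to rescue medication, curves are produced by "treatment and compared by log rank test". The effect estimate is described thus: "Hazard ratio will be estimated from cox proportional hazard model with treatment and period factors". Protocol 9.4.1.4 specifies the same log-rank comparisons and mentions no pairing.

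For Activity Limitation, SAP 10.1 states: "The ordinal activity limitation will be analyzed using Cochran-Armitage trend test".

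The data are paired by design. Sequence A is placebo then ubrogepant, sequence B the reverse (SAP 2.3). SAP 8.2 expects two treated events per participant, and SAP 2.4 notes that "some participants will contribute 2 qualifying prodrome events during the double-blind treatment period".

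Elsewhere the SAP models this dependence explicitly. The primary GLMM (SAP 8.3.3) has an unstructured covariance for the "residual effect for the repeated measurements (corresponding to the two qualifying prodrome events) within a participant". For the functional-disability GEE (SAP 8.4.1), "An unstructured working correlation matrix will be used for the repeated measures within each participant". SAP 8.1 adds a general rule: "All statistical hypothesis tests will be performed at the 2-sided 5% significance level".

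**The concern.** A two-group log-rank test, a Cox model with model-based variance and a Cochran-Armitage test all compute their variance as if the observations in the two groups were independent. Here the groups are largely the same people. The variance of a within-participant contrast contains a covariance term that these methods leave out.

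If a participant's two events tend to go the same way, which is the natural expectation for attacks in one person, the omitted term would reduce the variance. The reported p-values are then too large and the hazard-ratio intervals too wide. The hazard-ratio point estimate is not the difficulty; its stated precision is.

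Two things are at stake. Protocol 4.2 says the crossover was chosen for efficiency, and these analyses do not use it. The plan also gives the same diary data two incompatible error models. Rescue use, for example, is analysed with within-participant covariance as a proportion and without it as a time to event. A non-significant log-rank beside a significant GLMM could then reflect only the variance formula.

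**Working it through.** **The plan's own figures.** The documents give no operating characteristics for these tests. The stated sample size reproduces and is unaffected: 480/0.93 = 516.1, against 516, and 240 per intervention gives 97.6% power for 64% versus 80%, against at least 95%.

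**Inputs.** From the documents: two-sided 5% level, 1:1 allocation to two sequences, 48 hours of follow-up, eDiary times 1, 2, 3, 4, 6, 8, 24 and 48 hours. Assumed: the within-participant correlation, which is given nowhere, and 480 participants with both events. The 480 in the plan counts participants with a determinable primary endpoint, so using it for complete pairs is an assumption too.

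**Closed form (binary approximation).** For n pairs with equal variances and within-participant correlation r, the variance of the treatment difference is (2σ²/n)(1 − r). The unpaired analysis uses 2σ²/n. Its standard error is too large by the factor 1/√(1 − r), and the true two-sided error at nominal 5% is 2Φ(−1.96/√(1 − r)). With 40% having an event by 48 hours, latent correlations of 0.3, 0.5 and 0.6 correspond to binary correlations of 0.19, 0.33 and 0.41:

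| Binary r | 1/√(1 − r) | Effective critical value | True error |
|---|---|---|---|
| 0.19 | 1.11 | 2.18 | 2.9% |
| 0.33 | 1.22 | 2.40 | 1.7% |
| 0.41 | 1.30 | 2.55 | 1.1% |

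**Simulation A** (480 pairs, eDiary grid, 40% events, Gaussian copula, latent correlation 0.3 / 0.5 / 0.6; 1,500 trials per setting for the log-rank, 4,000 for the ordinal test). Under the null the log-rank rejected 2.7% / 1.3% / 1.0%, with a standard error about 13% / 25% / 35% too large. Cochran-Armitage on five levels rejected 2.2% / 0.9% / 0.5%. The log-rank figures agree with the closed form.

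**Simulation B** (separate code; 480 participants, exponential times with 64% event-free at 24 hours, censoring at 48 hours, Gaussian copula, 2,000 runs per null setting). Monte Carlo standard error at 5% is √(0.05 × 0.95/2000) = 0.5 percentage points.

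| Latent correlation | 0 | 0.2 | 0.4 | 0.6 |
|---|---|---|---|---|
| Log-rank, null rejection | 5.2% | 3.4% | 1.7% | 0.4% |
| Cox, model variance | 5.3% | 3.4% | 1.7% | 0.4% |
| Cochran-Armitage | 5.4% | 2.7% | 1.4% | 0.3% |
| Cox SE / true SE | 0.98 | 1.07 | 1.20 | 1.40 |
| Coverage of 95% Cox interval | 94.8% | 96.6% | 98.4% | 99.6% |
| Cox, participant-clustered robust | 5.3% | 5.0% | 5.6% | 4.6% |
| Paired ordinal score test | 5.3% | 4.3% | 4.9% | 5.0% |

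With 15% of second events missing, the log-rank rejected 3.2% / 2.1% / 0.6% at correlations 0.2 / 0.4 / 0.6. At a correlation of −0.2 the error rose to 6.4% (log-rank), 6.7% (Cox) and 6.9% (Cochran-Armitage).

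**Power.** This depends strongly on the assumed effect.

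- *40% versus 32.5% events (assumed).* The unpaired standard error is √[(0.40 × 0.60 + 0.325 × 0.675)/480] = 0.0309. At r = 0.19 / 0.33 / 0.41 the true standard error is 0.0278 / 0.0253 / 0.0238. Unpaired power is Φ[(0.075 − 1.96 × 0.0309)/true SE] = 70% / 72% / 73%. Correct power is Φ[0.075/true SE − 1.96] = 77% / 84% / 88%. Simulation A gave 68% / 74% / 73% against about 76% / 86% / 89%.
- *64% versus 72% event-free at 24 hours (assumed), latent correlation 0.4.* Simulation B (1,000 runs) gave 97.2% for the log-rank and 98.7% for the clustered Cox test.
- *64% versus 80% (planning assumption).* With 480 per treatment, z = 0.16/√[(0.64 × 0.36 + 0.80 × 0.20)/480] = 5.6, so there is almost no power to lose.

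**The case against.** The strongest reply is that little depends on these tests. Every affected endpoint is an additional one, outside the gatekeeping in SAP 12.0. The likely error is conservative, so it would not produce a false claim of benefit. Correlation-aware analyses of related outcomes are already planned: GLMMs for headache and prodrome symptoms by timepoint, for rescue use at 24 and 48 hours, and a responder GLMM for Activity Limitation. The size of the fault rests on a correlation the documents do not give. At zero it vanishes, and at 0.2 the standard error is only 7% too large. At the planning effect the power loss is negligible. The SAP also never rules out a robust variance, which may be intended. Finally, the log-rank test is written into the protocol.

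Most of this stands as a limit on importance. It does not make the methods right. The hazard ratios and p-values are prespecified and are to be set at the 5% level. Where the SAP wants within-participant dependence modelled it says so, down to convergence fallbacks for the GEE. A bare log-rank test and a Cox model with two named factors would be programmed with default variances. The GLMMs do not correct the hazard-ratio intervals or the ordinal test, which also omits period. The point about the protocol is correct and affects how the change is recorded.

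**Conclusion.** The concern holds. As written, the log-rank tests, Cox intervals and Cochran-Armitage test have their nominal properties only if a participant's two events are uncorrelated. For assumed latent correlations of 0.2 to 0.6, true type I error falls to between about 3% and 0.3%, and Cox standard errors are about 7% to 40% too large. The power cost ranges from negligible at the planning effect to roughly 7 to 15 percentage points by the closed form for 40% versus 32.5% events. Negative correlation would reverse the direction, but nothing in the documents suggests it. The primary and secondary analyses, the sample size and the family-wise error rate are unaffected. This should be corrected before the analyses are run, but it does not threaten the trial's main conclusions.

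**What to change.** For every time-to-event comparison in SAP 8.5, keep the Cox model with treatment and period, specify a robust sandwich variance aggregated by participant, and report the interval and treatment p-value from it in place of the plain log-rank p-value. Keep the Kaplan-Meier curves as drawn. This retains participants with only one event. A log-rank test stratified by participant is also valid but drops them, and in Simulation B it had less power even with all pairs complete (93.5% against 98.7% at correlation 0.4, 64% versus 72%).

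For Activity Limitation in SAP 10.1, replace the Cochran-Armitage test with a proportional-odds GEE with treatment and period, clustered on participant. This brings in a proportional-odds assumption, which the SAP should state.

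The cost is SAP wording, a participant identifier in the Cox code and one new ordinal model. No new data are needed. Because Protocol 9.4.1.4 names the log-rank test, the replacement should be entered in SAP Appendix F as a change from the protocol-planned analyses. The Cox models and the Activity Limitation method are specified only in the SAP.
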